3.6 Mortality data

Patient survival status will be monitored up to day 30 and tabulated in Table 9.

3.7 Additional data

Vital signs and cardiovascular monitoring will be documented at days 1, 3 and 5. (Table 12).

Table 1. Baseline characteristics

	FAS		IAS	
	Control	TRV027	Control	TRV027
	Median (range) or N (%)			
Age (yr)				
Age group				
<60				
60-69				
>69				
Gender				
Male				
Female				
BMI (kg/m²)				
Ethnicity				
White				
Mixed				
Asian				
Black				
Other				
Disease severity?				
Ie FDA grade 1-5?				

Table 2 Drug Compliance

	Control N (%)	TRV027 N (%)
Total Missed doses		
Total % Compliance		
Median missed doses per patient (range)		
Patients with missed dose due to hospital discharge		
Patients with missed dose due to death		

Table 3 Safety data – Pooled Adverse events

	Control		TRV-027	
	No. of Events	No. of Subjects*	No. of Events	No. of Subjects*
Number of Adverse events				
Severity				
Grade 1				
Grade 2				
Grade 3				
Grade 4				
Grade 5				
Missing				
AE classification				
Not serious				
Serious				
AE expectedness				
Expected				
Unexpected				
Not Applicable				
Missing				
Relation to study				
Definitely				
Probably				
Possibly				
Unlikely				
Not related				
Not assessable				
Missing				

* A patient may have several AEs

Table 4 – TRV027 Safety data –Adverse events details by patient

Control				TRV-027			
Pt ID	AE category	AE name	Grade	Pt ID	AE category	AE name	Grade

Table 6 Safety data – Serious Adverse Events

	Control		TRV027	
	No. of Events	No. of Subjects	No. of Events	No. of Subjects
Number of Serious Adverse Events				
Reasons for SAE				
Resulted in death				
Life threatening				
Congenital anomaly/birth defect				
Persistent or significant				
Disability/incapacity				
Inpatient hospitalisation/prolongation of existing				
Other				
Severity				
Mild				
Moderate				
Severe				
Life threatening				
Death				
Causal relationship to study drug				
Definitely				
Probably				
Possibly				
Unlikely				
Not related				
Not assessable				

Table 7 Safety data – Serious Adverse events details (Controls)

SAE description	SAE Term	Outcome

Table 8 Safety data – Serious Adverse events details (TRV027)

SAE description	SAE Term	Outcome

Table 9 Day 30 Survival

	Control	TRV027
Alive		
Dead		
Lost to follow-up		

Table 10 FAS Efficacy and exploratory parameters

	Control			TRV027		
	Day 1 [N=] Median (range)	Day 3 [N=] Median (range)	Difference D3 – D1	Day 1 [N=] Median (range)	Day 3 [N=] Median (range)	Difference D3 – D1
D-dimer						
Platelets						
aPTT						
INR						
Fibrinogen						
Total Bilirubin						
LDH						
Haptoglobin						
Creatinine						
BNP						
Troponin						
Ferritin						
Pro-calcitonin						
Glucose						

Table 11 Categorical Outcomes

	Control		TRV027		
	Day 1 (Yes/No %)	Day 3 (Yes/No %)	Day 1 (Yes/No %)	Day 3 (Yes/No %)	
Inotrope requirement					
DDimer response (>30% reduction)	NA		NA		

NA=not applicable

Table 12 vital signs and cardiovascular monitoring

	Screening [N=] % or Median (range)	Day 1 [N=] % or Median (range)	Day 3 [N=] % or Median (range)	Day 5 [N=] % or Median (range)
Pulse (Bpm)				
Diastolic blood pressure (mmHg)				
Systolic blood pressure (mmHg)				
Oxygen saturations (%)				
Temperature

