There were no serious adverse events attributed to TRV027 treatment. In the first cohort, one subject experienced hypotension necessitating dose reduction and then discontinuation of the study drug infusion. No other TRV027-related clinically significant adverse events were reported.

In the CP120027.2002 study (n= 621 patients with ADHF) which used doses ranging from 1-25 mg/hr for 48-96 hours, no safety issues were identified that affected the safety of trial subjects (NCT01966601). There was no difference from placebo in non-serious and serious treatment-emergent adverse events, events leading to discontinuation, or deaths.

Pharmacokinetics of TRV027

The pharmacokinetics of TRV027 has been studied in healthy volunteers, in patients with stable mild/moderate heart failure, patients with stable NYHA class III/IV CHF, and in 621 adults with acute decompensated heart failure. The clearance of TRV 027 is rapid (ranging between 51.3-127 L/hr) and exhibits a short half-life (4.2-15.8 minutes). Heart failure, sex, or renal dysfunction had no significant effect on the clearance of TRV027. TRV027 is not metabolized by, nor does it inhibit any of the CYP450 enzymes. The plasma protein binding of TRV027 is low at 53.4%.

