3. STUDY DESIGN

The proposed study will be run as a double-blind, randomized controlled experimental medicine study in male and female hospitalised patients (n=60) aged 18 or over, with confirmed COVID-19 infection. Patients who are admitted with confirmed COVID-19 infection will be screened with a routine medical assessment (see Table 1) and enrolled if they meet the eligibility criteria. Subjects will be block randomised based on age to continuous intravenous infusion of placebo or TRV027 for 7 days.

Day 1 procedures can occur on the same day of screening and include a venous blood test prior to commencing an intravenous infusion of either placebo (250ml sodium chloride 0.9%) or TRV027 in 250ml sodium chloride 0.9% at 12mg/hr. The infusions will continue for 7 days. Venous blood tests will be repeated at days 3, 5 and 8 amounting to approximately 120mLs of blood in total over the 8-day period.

Once the infusion has finished, the subjects will remain in hospital for a further 24 hours for vital signs and adverse event monitoring. If the infusion is stopped before the 7-day dosing period finishes, they will be advised to remain in hospital for a 24-hour period for monitoring during which time the study assessments will continue. If discharge is planned for day 6 or 7 the day 8 blood tests can be taken on the day of discharge. They will also be followed up at Day 30 either by telephone call or through examination of medical records.

Table 1: Schedule of Study Events

Study Day	*Screening	*1	2	3	4	5	6	7	8	9	30
Informed consent (or agreement from consultee if incapacitated)	X										
Eligibility assessment; routine medical assessment (history, observations)	X										
Review of Concomitant Medications ¹		X	X	X	X	X	X	X	X		
Pregnancy test (If appropriate)	X										
Venous blood test for primary and exploratory endpoint assessment:											
D-dimer		X		X		X			X		
Platelets		X		X		X			X		
aPTT		X		X		X			X		
INR		X		X		X			X		
Fibrinogen		X		X		X			X		
Plasma Renin Mass		X									
Total Bilirubin		X		X		X			X		
LDH		X		X		X			X		
Haptoglobin		X		X		X			X		
Creatinine		X		X		X			X		
BNP		X		X		X			X		
Troponin		X		X		X			X		
Ferritin		X		X		X			X		
Pro-calcitonin		X		X		X			X		
Glucose		X		X		X			X		
Clinical assessment for exploratory endpoints											
Inotrope requirement		X		X		X			X		
GCS		X		X		X			X		
SOFA score		X		X		X			X		
Randomisation		X									
Infusion		X	X	X	X	X	X	X	X		
Vital signs monitoring four times a day		X	X	X	X	X	X	X	X	X	

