Adverse event monitoring		X	X	X	X	X	X	X	X	X	
Telephone call or medical record check											X

[figure not shown]
*Screening and day 1 can be combined

1. All concomitant medications will be reviewed at baseline but only those which affect eligibility or are associated with AEs will be recorded for subsequent days in the Ecrf. ACEi and aldosterone antagonists will be recorded.

Dose Rationale

TRV027 has been studied in patients with acute heart failure in doses ranging from 1.25 – 31.25 mg/hr. Using in vitro-derived AT1R receptor binding data as well as population PK data in healthy volunteers, simulations were performed to explore a range of doses of TRV027 which might be expected to result in at least 80% receptor occupancy, correcting for protein binding. The results (Figure 1) suggest that 12 mg/hr will result in median receptor occupancy well in excess of 80%. This dose is in the mid-range of what has been studied clinically and is expected to be well tolerated.

Figure 1: Estimation of the median AT1R receptor occupancy resulting from TRV027 given at a dose of 12 mg/hr for 96 hours

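### SAP 3.7 and Table 12 end the vital-signs summary at Day 5, so the last 48–72 h of a full 168 h infusion and all post-infusion monitoring have no planned summary

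*SAP*

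**What the plan says.** SAP 3.7: "Vital signs and cardiovascular monitoring will be documented at days 1, 3 and 5". The shell headed "Table 12 vital signs and cardiovascular monitoring" has four time columns (Screening, Day 1, Day 3, Day 5) and rows for pulse, diastolic and systolic blood pressure, oxygen saturation and temperature. It names no analysis population.

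Protocol 3, on treatment: "The infusions will continue for 7 days". Table 1 of the protocol marks infusion on Days 1 to 8, and it marks the row "Vital signs monitoring four times a day" on Days 1 to 9. After the infusion, "the subjects will remain in hospital for a further 24 hours for vital signs and adverse event monitoring". Early discharge is foreseen: "If discharge is planned for day 6 or 7 the day 8 blood tests can be taken on the day of discharge".

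Protocol 5.2 treats routine observations as study endpoints and does not record them separately as adverse events. Non-serious events below CTCAE grade 3–4 are normally not regarded as clinically significant for adverse-event reporting.

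SAP 2.2 defines the analysis population as full-course patients and places those with less than 3 days of infusion in the baseline data set. SAP 2.5 keeps withdrawn patients, including those withdrawn for toxicity, in the final analysis.

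**The concern.** The protocol collects vital signs throughout the infusion and for a day after it, but the SAP tabulates them only to Day 5. The protocol attributes vasodilatory properties to TRV027 (section 1.1), so blood pressure is a natural safety measurement to summarise in full. In the largest earlier study the infusion lasted at most 96 h, against 168 h planned here.

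The adverse-event tables do not fully replace the missing columns. If routine observations include blood pressure, as seems reasonable, Protocol 5.2 would normally keep a modest, non-serious fall out of them. Table 12 is the only SAP table with blood-pressure rows, so a modest difference between arms would be seen mainly there. After Day 5 there is no column in which to see it.

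The unstated population adds to this. If Table 12 follows SAP 2.2, patients whose infusion stopped early could be left out of the blood-pressure summary.

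**Working it through.** **Inputs.** Infusion length: 7 days (Protocol 3). Vital-signs days: 1 to 9 (Protocol Table 1). SAP days: 1, 3 and 5 (SAP 3.7 and Table 12). Longest human infusion cited: 96 h (Protocol 1.3). Planned sample: 60 patients. The SAP states no figure for coverage, so there is none to reproduce.

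**1. Schedule against table.**

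| Study day | Protocol plan | Column in Table 12 |
|---|---|---|
| 1, 3, 5 | Infusion, vital signs | Yes |
| 2, 4 | Infusion, vital signs | No |
| 6, 7 | Infusion, vital signs | No |
| 8 | Infusion ends, vital signs | No |
| 9 | Post-infusion vital signs | No |

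Three of nine scheduled days have a column. Days 2 and 4 lie between summarised days, so their absence matters little. The point concerns Days 6 to 9.

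**2. Hours of infusion after the last column.** Full course = 7 × 24 = 168 h. Let the infusion start t hours into Day 1, with 0 ≤ t ≤ 24. Calendar Day 5 ends 120 − t hours after the start, which is 96 to 120 h. Infusion remaining = 168 − (120 − t) = 48 + t, which is 48 to 72 h.

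**3. Post-infusion period.** The infusion ends t hours into Day 8, and the 24 h of monitoring run into Day 9. Table 12 has no column for either day, so none of the 24 h is summarised.

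**4. Early discharge.** Assume that the infusion stops 24 h before discharge. The protocol only advises patients to stay that long, so this is an assumption. Discharge on Day 6 means stopping during Day 5, which leaves 0 h of infusion after Day 5. Discharge on Day 7 means stopping during Day 6, which leaves 0 to 24 h. The 48–72 h figure therefore applies to full-course patients only.

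**5. Relation to earlier human exposure.** Planned time beyond 96 h = 168 − 96 = 72 h. Of this, Table 12 can include (120 − t) − 96 = 24 − t, which is 0 to 24 h.

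**6. Do Days 3 and 5 capture steady exposure?** Yes. The stated half-life is 4.2 to 15.8 min, so five half-lives are 5 × 4.2 = 21 min to 5 × 15.8 = 79 min. By then 1 − 0.5⁵ = 96.9% of plateau is reached, assuming single-phase first-order kinetics. What the table lacks is longer duration and the period after stopping.

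**The case against.** The strongest reply is that the safety data are already well covered. Clinically significant events are recorded until 24 h after the infusion and reported by arm (Protocol 5.2, SAP 3.4). Dose interruptions are reported per patient (SAP 3.5). Inotrope requirement is shown by arm at Days 1 and 3 (Table 11). SOFA, which includes blood pressure, falls under the between-group comparison at Days 3, 5 and 8 in the prose of SAP 3.3, although no table shell has a SOFA row. The DSMC reviews safety data after every 12 patients. All of this stands, and it keeps the point minor. What remains is the summary of the measurements themselves: shifts in blood pressure that no investigator judges clinically significant.

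Three stronger readings are tempting, and the documents do not support them.

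- *A late hypotensive effect would be missed.* A reader might link the gap to the earlier hypotension case that led to discontinuation. That case arose in a cohort whose whole regimen lasted 4 + 10 = 14 h, so a similar onset here would fall on Day 1 or 2. The 621-patient study found no difference from placebo in adverse events, discontinuations or deaths. Infusions of up to 14 days were well tolerated in rats and dogs. Nothing cited points to a late or duration-dependent effect.
- *The SAP pools the arms.* Table 12 shows no Control/TRV027 header in the text available, and SAP 3.7 does not mention arms. However, that text breaks off inside Table 12, and Table 5, which SAP 3.4 cites, is also absent. A header may simply have been lost. The original must be checked before anything is concluded.
- *Vital signs are not collected after Day 5.* They are, through Day 9 under the protocol. Only the planned summary stops.

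Which of the four daily readings is tabulated is also unstated. That is table-specification detail and adds no weight.

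**Conclusion.** The point holds as a gap in schedule coverage. SAP 3.7 and the Table 12 columns agree on the Day 5 limit, so it does not come from a damaged table. For a full course, 48–72 of 168 h of infusion and all 24 h of planned post-infusion monitoring have no summary column. For patients discharged on Day 6 or 7, the uncovered infusion time is 0 to 24 h under the assumption in the working.

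These hours measure what the table leaves out, not a lost signal. The argument assumes that routine observations in Protocol 5.2 include blood pressure. It does not depend on whether Table 12 has an arm header. This is a minor improvement to safety reporting, with no effect on data collection, the primary D-dimer analysis or the sample size.

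**What to change.** Extend SAP 3.7 and Table 12 to Day 8, and to Day 9 where available, with N in each column. State in SAP 3.7 that the table is presented by Control and TRV027, after checking whether the original shell already has that header. State also that it covers all patients who received any infusion, not only full-course patients. This settles SAP 2.2 against SAP 2.5 for this table. Keep it descriptive, without tests. A footnote naming the daily reading used would help but is optional.

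The cost is a sentence or two in SAP 3.7 and an edited shell. SAP 2.3 says that most, not all, data are in REDCap, so some later readings may need transcription from source. At one reading a day this is at most 2 columns × 60 patients = 120 sets, and fewer after discharges. The later columns will describe a smaller, selected group because of discharge, which is the reason for showing N and for not testing.
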